1. OBJECTIVES

1.1 Study Design

The study is a randomized trial of the Jacki® recovery jacket garment versus usual care for post-discharge pain management in patients who had mastectomy and reconstructive surgery in one or both breasts.

1.2 Primary Objectives

1. Compare pain intensity on a 0-10 numeric scale at the post-surgical follow-up clinic when all surgical drains are removed between usual care pain management (UC) and “Jacki” plus usual care (Jacki) groups.

1.3 Secondary Objectives

1. Explore differences in health related quality of life (HRQOL) and breast symptoms between groups at the follow-up clinic.
2. Evaluate at-home (from discharge to follow-up) pain patterns and pain management by group.
3. Evaluate patient-reported Jacki usage frequencies in the intervention group.

2. BACKGROUND

2.1 Study Disease(s) and Health Setting

Patients have mastectomy either in treatment for breast cancer or as prophylaxis, and may have reconstructive surgery at the same time. In 2016, it is estimated that 246,660 new cases of invasive breast cancer will be diagnosed in women in the U.S. along with 60,290 cases of in situ breast cancer.¹ Treatment options for early-stage breast cancer are generally breast conserving surgery with adjuvant radiation or mastectomy. An analysis of the National Cancer Database published in 2015² found that national rates of mastectomy for early-stage breast cancer rose from 34.3% in 1998, the first year in the study, to 37.8% in 2011, the last year, with much of the increase in the last eight years. Rates of reconstructive surgery in patients having mastectomy rose from 11.6% in 1998 to 36.4% in 2011. During the same period, the rate of patients with unilateral breast cancer who elected contralateral prophylactic mastectomy (CPM) rose from 1.9% to 11.2%,² a trend that will likely continue³ despite lack of evidence favoring CPM outside a high risk setting.⁴ Rates of bilateral prophylactic mastectomy (BPM) for those with no cancer diagnosis but genetic and/or family risk are more difficult to estimate due to lack of cancer diagnosis and registry, but studies have estimated these surgeries may be in the hundreds to thousands per year in the U.S.^{5,6} and expected to increase with increased awareness of genetic breast cancer and increased uptake of genetic testing.⁶

2.2 IND Agent(s)

Not applicable.

2.3 Other Agent(s)

Not applicable.

2.4 Rationale

Patients who have mastectomy and reconstructive surgery often experience discomfort from not only the surgical incisions, but also from the drainage tubes inserted at the incision sites. The tubes and drainage receptacles are often difficult to manage when patients are discharged from the hospital, wearing typical clothing and returning to regular daily activities.

Most women are able, at the time of mastectomy, to have breast reconstruction surgery to rebuild and contour breast shape. Post-operative care is more complex than mastectomy alone and requires an inpatient stay of two to four nights. The accumulation of fluid – a *seroma* – is a frequent complication following breast surgery and warrants the insertion of drainage tubes for prevention. In a review investigating techniques in the prevention and management of seromas after breast surgery, drains produced a significant reduction in seroma incidence.⁷ The number of drains depends on the type of surgery and preference of the surgeon and ranges from 2 for unilateral and from 4 for bilateral mastectomy.^{8,9} Patients after mastectomy and breast reconstruction experience soreness in the chest, underarm and shoulder, as well as numbness at the drainage site. Patients have reported the greatest discomfort at the drain insertion sites. The number of drains after mastectomy has also been associated with increased pain in the post mastectomy patient, although the number of drains was not associated with the rate or number of seromas.^{8,10} If axillary lymph nodes are removed, patients may experience some numbness in the arm and also are at risk for *lymphedema*,¹¹ a build-up of lymph that causes swelling in the arm, hand, breast, underarm, chest, trunk and/or back.

Post-operative pain experienced by women undergoing mastectomy and breast reconstruction can contribute to limited range of motion in the upper body, resulting in worsening stiffness and edema that have a negative impact on quality of life (QOL) and activities of daily living (ADL). It is vital that early upper body exercise and movement is performed to prevent lymphedema or swelling.¹² Increased activity can reduce the side effects of surgery, shorten recovery time, and ultimately improve long-term outcomes.^{13,14} This was demonstrated in a study of 35 post-operative mastectomy patients randomized to participate in an early physical rehabilitation program: participants in the program reported significant improvement in pain reduction and QOL.¹⁵ Consequently, studies have demonstrated that inadequately managed pain in the acute post-operative period is one of the greatest predictors of chronic pain syndromes in breast surgery patients.¹⁶⁻²¹

Traditional clothing options for women post mastectomy are undergarments such as post mastectomy camisoles, tank tops, and customized mastectomy bras. Camisoles are usually worn as nightwear or under loose fitting clothing until surgical drains are removed. The Jacki is a post mastectomy garment that was developed by a breast cancer survivor as a means to manage and hold the drainage system. The jacket is professionally manufactured, made with high quality material (cotton and Polartec® microfleece), and is suitable for business casual attire. Anecdotally-reported patient experiences suggest that use of the Jacki immediately after surgery is an early intervention that may reduce pain and prevent activity limitations over time.^{22,23} The Jacki is unique as outer apparel that can be worn in the workplace, at social events, and during usual activity, and that allows full range of motion. The Jacki allows the patient to discreetly place drainage tubes in hidden and secure inside pockets that reduce the possibility of dislodgement and pulling. Velcro sleeves allow for easy access when patients return for follow-up appointments that require taking blood pressure, IV access, injections and medical exams. In particular, women have described²⁴ how the Jacki has put them at ease when in public venues that otherwise would have created feelings of vulnerability and self-consciousness because of body changes and functional limitations from surgery.

2.5 Preliminary Data

A preliminary survey study was conducted to explore self-reported pain intensity levels (just before discharge to ambulatory care) in patients post mastectomy in the Boston area. The sample (n=88) had a nearly equal distribution of age above and below 50 years; most were college educated and married/partnered. Of the 88 participants, 39% reported moderate to severe pain intensity, 53% reported pain several times a week to constantly, and 34% reported pain intensity as fair to almost unbearable soon after surgery. Sixty percent of participants had received a bilateral mastectomy, and 43% of these had bilateral implant reconstruction. Mean scores on the 0-10 pain intensity scale were 5.26 (SD=2.28) for those who had bilateral mastectomy and 2.5 (SD=2.13) for those having single mastectomy; participants who had reconstruction at the time of surgery pain averaged 4.98 (SD=2.18).

3. PARTICIPANT SELECTION

3.1 Eligibility Criteria

1. Patients who are \geq 18 years old.
2. Patients who speak and understand English.
3. Patients who have had mastectomy with reconstructive surgery in one or both breasts.

3.2 Exclusion Criteria

1. Co-morbid delirium, dementia, mental illness, or neurocognitive deficit prohibiting informed consent and/or ability to complete study procedures.

3.3 Inclusion of Women and Minorities

The sample will be entirely women (although men are at risk for, or diagnosed with, breast cancer, they do not have reconstructive surgery post mastectomy). English-speaking women of all races and ethnic groups are eligible and will be recruited for this trial.

4. REGISTRATION PROCEDURES

4.1 General Guidelines for DF/HCC Institutions

Institutions will register eligible participants in the Clinical Trials Management System (CTMS) OnCore. Registrations must occur prior to the initiation of protocol therapy (i.e., discharge from the hospital). Any participant not registered to the protocol within this timeframe will be considered ineligible and registration will be denied.

A member of the study team will complete the protocol-specific eligibility checklist.

4.2 Registration Process for DF/HCC Institutions

DF/HCC Standard Operating Procedure for Human Subject Research Titled *Subject Protocol Registration* (SOP #: REGIST-101A for Centralized Registration) must be followed. Research staff at enrolling institutions will fax the signed informed consent form and eligibility checklist to the protocol registrar at the Office of Data Quality (ODQ) at [contact], who will confirm eligibility and complete centralized registration of the participant in OnCore.

4.3 General Guidelines for Other Investigative Sites

Not applicable.

4.4 Registration Process for Other Investigative Sites

Not applicable.

5. TREATMENT AND/OR IMAGING PLAN

5.1 Treatment Regimen

5.1.1 Enrolling Sites and Study Entry

A sample of 130 women who have had or will have mastectomy with reconstruction will be recruited.

Screening will be conducted by a research team member using the clinical surgery and post-op schedule to identify eligible patients. A clinical care nurse or clinical research associate who is a member of the research study team will invite the participant to hear about the study, and if the patient agrees to participate, will consent the participant. The research team member will complete the eligibility checklist.

The research team member will fax the consent form and eligibility checklist to the Office of Data Quality to register the participant and will receive the participant's randomized study group assignment. Participants will be randomly assigned in blocks of random permuted size, stratified by site and unilateral vs bilateral mastectomy, to the usual care pain management (UC) or "Jacki" plus usual care (Jacki) groups.

The research team member will meet the participant in the hospital on the first day post-surgery (or second day, if the patient is too sick, has a surgical complication, or is in too much pain or distress to be approached the first day) to collect the baseline (T1) questionnaire and will provide the post-discharge daily diary questionnaires (T2) to the participant, answer questions, and make arrangements for collection of the follow-up questionnaire (T3) with the participant at the clinic visit when all the post-surgical drains are removed. The research team member will telephone or email the participant at home the first or second day after discharge to remind her to fill out the T2 daily questionnaire; if the participant has multiple follow-up visits before all drains are removed, the research team member may also telephone, email or meet the participant at follow-up visits to remind her to continue filling out the T2 daily questionnaire until all drains are removed.

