13.2 Sample Size, Accrual Rate and Study Duration

The primary objective of this study will be to compare pain intensity (measured on the 0-10 scale, PINS) at the follow-up clinic appointment when all drains are removed (T3) between those randomized to UC or Jacki groups. A reduction of 1.0 on the PINS is thought to be clinically significant. With a sample size of 130 there is 80% power to detect a 1-point difference in PINS between UC and Jacki groups using a Wilcoxon rank sum test at the 2-sided 0.1 significance level assuming a standard deviation of 2.2 from

the preliminary study. The following table depicts the impact on power if the standard deviation at the follow-up visits is smaller or larger than estimated.

Standard Deviation	Power
1.8	91%
2.0	86%
2.2	80%
2.4	74%
2.6	68%

With a projected 13% rate of attrition, a total of 149 participants enrolled will yield an analytic sample of 130 evaluable participants. This number of participants will be accrued and will complete data collection within 10 months, based on clinical volume .

Accrual Targets				
Ethnic Category	Sex/Gender			
	Females	Males	Total	
Hispanic or Latino	39	+ 0	=	39
Not Hispanic or Latino	91	+ 0	=	91
Ethnic Category: Total of all subjects	130	+ 0	=	130
Racial Category				
American Indian or Alaskan Native	0	+ 0	=	0
Asian	6	+ 0	=	6
Black or African American	13	+ 0	=	13
Native Hawaiian or other Pacific Islander	0	+ 0	=	0
White	111	+ 0	=	111
Racial Category: Total of all subjects	130	+ 0	=	130

No interim analyses are planned due to the short duration, minimal risk, and minimal burden of the study. There are no early stopping rules.

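### Section 5.1.1 and the accrual table set recruitment at 130, but Section 13.2 needs 149 enrolled for 130 evaluable; stopping at 130 leaves about 113 evaluable and 75–76% power instead of 80%

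*Combined protocol and SAP*

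**What the plan says.** The enrolment number appears in three places.

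- Section 5.1.1, which describes screening, consent, registration and randomisation: "A sample of 130 women who have had or will have mastectomy with reconstruction will be recruited".
- Section 13.2, text: "With a sample size of 130 there is 80% power to detect a 1-point difference in PINS", with the test and level given as "using a Wilcoxon rank sum test at the 2-sided 0.1 significance level". It continues "With a projected 13% rate of attrition" and concludes that "a total of 149 participants enrolled will yield an analytic sample of 130 evaluable participants". The next sentence says that this number will be accrued within 10 months.
- Section 13.2, Accrual Targets table: the ethnicity rows sum to 39 + 91 = 130. The race rows sum to 6 + 13 + 111 = 130, shown against "Racial Category: Total of all subjects".

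Section 13.5 limits the primary analysis to randomised participants who reported a T3 pain score and rules out imputation.

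**The concern.** In the text of Section 13.2, 130 is what remains after attrition. In Section 5.1.1 and the accrual table the same 130 is the number of women entering the study. Both cannot hold unless nobody is lost, and 13.2 projects 13% losses. Section 13.2 also disagrees with itself, since its text enrols 149 and its table adds to 130.

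The number matters because attrition passes straight into the primary test: without a T3 score a participant is not analysed. No interim analysis is planned, and the documents describe no sample-size re-estimation that could make up a shortfall. The design is set at 80% power for the assumed SD, so there is no margin to absorb one. Someone tracking enrolment against 5.1.1 or the accrual table could reasonably close the study 19 participants short (149 − 130).

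**Working it through.** **Inputs**

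- Difference to detect: 1.0 point on the 0–10 scale (13.2: "A reduction of 1.0 on the PINS is thought to be clinically significant").
- SD: 2.2 (13.2: "assuming a standard deviation of 2.2 from" the preliminary study), with 1.8 to 2.6 in the sensitivity table.
- Test and level: Wilcoxon rank sum, two-sided 0.10 (13.2).
- Attrition: 13% (13.2).
- Allocation: 1:1. This is an assumption, as no ratio is stated.

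**Step 1: reproduce the plan's power table**

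Noether's formula for the Wilcoxon test, with a normal shift and equal arms, is

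p = Φ(δ / (SD·√2)), power = Φ(√(3N)·(p − 0.5) − 1.645).

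At SD 2.2, p = Φ(1/3.111) = 0.626. With N = 130, √390 × 0.126 − 1.645 ≈ 0.844, so power = 80.1%.

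| SD | Plan | Noether, N = 130 | Noether, N = 113 |
|---|---|---|---|
| 1.8 | 91% | 91.5% | 87.9% |
| 2.0 | 86% | 86.1% | 81.6% |
| 2.2 | 80% | 80.1% | 75.0% |
| 2.4 | 74% | 74.0% | 68.7% |
| 2.6 | 68% | 68.1% | 62.9% |

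The plan's column agrees with N = 130 to within rounding or half a point in every row. The 80% therefore belongs to 130 analysed, not to 130 recruited.

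**Step 2: check the attrition allowance**

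130 / (1 − 0.13) = 149.4, and 149 × 0.87 = 129.6, or about 130. The 149 in 13.2 is right to rounding.

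**Step 3: apply the same attrition to 130 recruited**

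130 × 0.87 = 113.1, so 113 evaluable.

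**Step 4: power at 113 (SD 2.2)**

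√339 × 0.126 − 1.645 ≈ 0.676, so power = 75.0%. Other approximations, each compared with its own value at 130:

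| Method | N = 130 | N = 113 |
|---|---|---|
| Noether | 80.1% | 75.0% |
| Normal approximation, n × 3/π | 81.3% | 76.3% |
| Noncentral t, n × 3/π | 80.9% | 75.8% |
| Simulated Wilcoxon, continuous scores | 81.1% | 75.4% |
| Simulated Wilcoxon, scores rounded to 0–10 | 79.8% | 75.3% |

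The simulations used 20,000 replicates and a control mean of 5, which is an assumption. Within each method the loss is about 5 points (4.5 to 5.7).

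**The case against.** The strongest reply is that Section 13.2 is where the sample size is set, and its derivation is complete and correct. It starts from 130 evaluable, adds 13% and reaches 149, and its sentence about accruing this number most naturally means 149. On that reading, 130 was carried unlabelled into 5.1.1 and the table, 5.1.1 states no cap, and no power is lost. The loss is also modest: the plan's own table already shows 74% if the SD is 2.4. Section 13.5 expects little missing data, and lower attrition would leave more than 113.

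Much of this stands. The calculations in 13.2 contain no error; the fault is an inconsistency between figures. The power loss is conditional on 130 governing. Whether 130/0.87 is written as 149 or 150 is immaterial.

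It does not remove the problem. The plan does not say that the text of 13.2 takes precedence, and the conflicting table sits in that same section under the title of accrual targets. The expectation of little missing data does not replace the 13% that 13.2 chose for planning. An SD larger than assumed would reduce power further: at SD 2.4 with 113 evaluable it is 68.7%.

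**Conclusion.** The concern holds. The current text states the enrolment target as both 130 and 149, and only 149 is consistent with the stated 80% power. Recruiting 130 would leave about 113 evaluable and 75–76% power: 75.0% by the formula that matches the plan's table, and up to 76.3% by the others. This rests on the plan's 13% attrition, its SD of 2.2 and 1.0-point difference, and an assumed 1:1 allocation. If 149 are enrolled, about 130 are evaluable and the 80% is kept. The point should be corrected, but it does not undermine the design.

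**What to change.** Use one enrolment figure throughout.

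- In Section 5.1.1, give 149 as the number to be enrolled and identify 130 as the expected evaluable sample.
- Rescale the Accrual Targets table to 149. Keeping the present proportions (× 149/130 = 1.146), ethnicity becomes 39 → 45 and 91 → 104 (total 149). Race becomes 6 → 7, 13 → 15 and 111 → 127 (total 149).

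If accrual is in fact limited to 130, leave those entries and revise the text of 13.2 to about 113 evaluable with 75–76% power. The power table should then be recomputed at 113; the Noether column above gives the values.

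The first option costs one sentence and one table. It asks for no more participants than 13.2 already intends and leaves the analysis unchanged.

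### The described workflow releases the arm before the self-reported T1 baseline is collected, so T1 is unprotected in the supplementary analyses that use it; the primary T3 test is unaffected

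*Combined protocol and SAP*

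**What the plan says.** **Order of steps.** Section 5.1.1 runs from screening through consent and the eligibility checklist to a fax to the registration office, on which the team member "will receive the participant's randomized study group assignment". The next paragraph begins: "The research team member will meet the participant in the hospital on the first day post-surgery". That visit is where T1 is collected. It may move to the second day for several reasons, one being that the patient "is in too much pain or distress to be approached the first day".

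**Deadline.** Section 4.1 sets the only explicit limit: "Registrations must occur prior to the initiation of protocol therapy (i.e., discharge from the hospital"). It gives no order relative to T1 or to surgery. Neither the registration sections, the study calendar nor Section 13 adds one, and no section describes blinding or says when a participant learns her arm.

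**Who may enter.** Section 5.1.1 says "A sample of 130 women who have had or will have mastectomy with reconstruction will be recruited". Criterion 3 in Section 3.1 says "Patients who have had mastectomy with reconstructive surgery in one or both breasts". Section 4.2 has the registrar confirm eligibility before completing registration. Sections 5.1.1 and 13.3 stratify by site and by unilateral or bilateral mastectomy, without saying whether laterality is as planned or as performed.

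**Use of T1.** Section 13.5 makes the primary test a Wilcoxon rank sum test on T3 pain. ANCOVA is optional, with the baseline score and laterality among its candidate factors, and linear mixed models of pain over time are planned. Section 13.6 plans T1-T3 change for the secondary measures collected at both times.

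**The concern.** A baseline serves as a covariate or an anchor because assignment cannot have influenced it. A jacket compared with usual care cannot be hidden from the wearer, and T1 pain is her own rating. If she knows her arm when she fills in T1, disappointment or expectation could shift her answer. If staff know it, the choice between day 1 and day 2 could also vary by arm, and pain soon after surgery may differ between those days.

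An arm-related shift in T1 would carry into each analysis that conditions on T1 or measures change from it. Those analyses are supplementary, but they would be reported beside the primary result and could be read as confirming or qualifying it.

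A second, smaller matter sits in the same section. Recruiting women whose surgery lies ahead, under a criterion that requires surgery to be done, leaves it unclear whether anyone could be randomized before the operation. If so, the laterality stratum would rest on the plan rather than on what was done.

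**Working it through.** **1. Is the order stated or inferred?** In 5.1.1 the assignment is received at registration and T1 is described afterwards. The only rule (4.1) is registration before discharge. Under that rule, T1 followed by assignment complies, and so does assignment followed by T1. The described workflow is the second; no sentence forbids the first.

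**2. Which analyses use T1?**

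| Analysis | Section | Status | Uses T1? |
|---|---|---|---|
| Wilcoxon test (or alternative t-test) on T3 pain | 13.5 | Primary | No |
| ANCOVA on T3 pain | 13.5 | Optional | Yes, baseline score a candidate |
| Linear mixed model of pain over time | 13.5 | Planned | Yes, if T1 is included as the first time point |
| T1-T3 change, secondary measures taken at both times | 13.6 | Planned | Yes |

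**3. Does the plan's own figure depend on T1?** Inputs from 13.2: 130 evaluable, difference 1.0, SD 2.2, two-sided alpha 0.10. Equal allocation (65 per arm) is my assumption. With the Wilcoxon efficiency factor 3/π under normality, the effective n per arm is 65 × 3/π = 62.07. The noncentrality is 1.0 / (2.2 × √(2/62.07)) = 2.53, which gives power 0.813; a simulation of the Wilcoxon test gave 0.80. The stated 80% reproduces. Attrition: 130 / 0.87 = 149.4, against the stated 149. Neither T1 nor the stratum enters, so reordering the steps changes neither figure.

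**4. Illustrative ANCOVA bias.** The documents give neither a T3-on-T1 slope nor an arm-related reporting shift, so both are assumptions. If knowledge of arm shifts reported T1 in one arm by *b* and leaves T3 unchanged, the adjusted difference is displaced by slope × *b*:

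- lowest: 0.3 × 0.3 = 0.09 points
- highest: 0.7 × 0.5 = 0.35 points

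For the effect on a nominal 0.10 test with no true difference, assume also SD 2.2 at both times, so that the slope equals the correlation *r*. The standard error is 2.2 × √(2/65) × √(1 − *r*²).

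| Slope | Shift | Bias | SE | Bias/SE | Actual type I error |
|---|---|---|---|---|---|
| 0.3 | 0.3 | 0.09 | 0.368 | 0.24 | 0.11 |
| 0.5 | 0.5 | 0.25 | 0.334 | 0.75 | 0.19 |
| 0.7 | 0.5 | 0.35 | 0.276 | 1.27 | 0.36 |

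The sign could go either way. Reported T1 that is too high in the Jacki arm makes ANCOVA overstate benefit; reported T1 that is too low makes it understate benefit. These figures do not transfer to the mixed model, whose form the plan does not give, or to the secondary pain items, which use 5-point scales.

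**5. Laterality.** In the preliminary survey (2.5), mean pain was 5.26 after bilateral and 2.5 after single mastectomy, a gap of 5.26 − 2.5 = 2.76 points just before discharge. The factor is worth balancing well, although that gap was not measured at T3. A stratum recorded from the wrong source weakens this balance but does not bias a randomized comparison.

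**The case against.** The strongest reply is that the order is only narrative. Section 4.1 already permits T1 first, 5.1.1 does not say that the same person receives the assignment and collects T1, and nothing says the participant knows her arm at that visit. Jacket instruction is described separately in 5.1.2, the treatment period starts at discharge, and T1 is a pen-and-paper self-report, which limits what staff knowledge alone could do. All of that stands, and it means bias is possible rather than shown. It does not close the gap: the plan describes the unprotected order and contains no safeguard against it.

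Four stronger readings are tempting and are not supported:

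- *The primary result is at risk.* It is not. The T3 test uses neither T1 nor the stratum, and setting an assumed ANCOVA bias against the 1.0-point target should not suggest otherwise.
- *A T1-T3 change score in 0-10 pain would carry the full shift.* No such score is specified. Section 13.6 applies change to secondary measures, and 13.5 assigns pain over time to mixed models.
- *Women are randomized before surgery.* Section 5.1.1 speaks of recruiting them. Criterion 3, applied at the registrar's eligibility check in 4.2, would keep randomization after the operation. What remains is a contradiction in wording and an undefined source for the stratum.
- *A wrong stratum biases the comparison.* It costs balance only. Surgery details are recorded from the medical record at T1 (5.1.3), so performed laterality remains available as a covariate.

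**Conclusion.** The point holds in limited form and should be corrected. As described, T1 is collected after the assignment has been received in an unblinded trial, and nothing protects it. The consequence is confined to the optional ANCOVA, the mixed model and the T1-T3 change in secondary measures. The primary comparison, the sample size and the power stand.

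The size and direction of any bias are unknown. The range of 0.09 to 0.35 points for ANCOVA rests wholly on an assumed slope of 0.3 to 0.7 and an assumed shift of 0.3 to 0.5 points; it shows what could happen and is not an estimate. The mismatch between 3.1 and 5.1.1 is a drafting contradiction, largely contained by the eligibility check, and should be settled in the same amendment.

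**What to change.** 1. In 4.1 and 5.1.1, state that T1 is collected after surgery, on day 1 or 2 as now, and before the assignment is requested or released to staff or participant, with registration still completed before discharge.
2. Add that a woman who cannot complete T1 in time may still be registered, with T1 recorded as missing. The primary analysis needs only a T3 score, so T1 should not become a condition of entry.
3. Reconcile 5.1.1 with criterion 3: women may consent before surgery but are randomized only after it.
4. In 5.1.1 and 13.3, state that the laterality stratum is taken from the operation performed.

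This reorders existing steps in a short amendment and adds no visit. The cost is time: Section 2.4 gives an inpatient stay of two to four nights, and with T1 on day 2 there is less room to register by fax, receive the assignment and teach jacket use before discharge. The targets of 130 evaluable and 149 enrolled, and the power of about 80%, do not change.
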